9. NON-STANDARD DATA DERIVATION RULES AND STATISTICAL METHODS

The following sections describe additional derivation rules and statistical methods which are not presented in section 10.1.

9.1. Data derivation

9.1.1. Demography

- For computation of age, following rule need to be considered:
 - Age will be calculated as the number of years between the date of birth and the date of first vaccination.
 - To ensure that the collection of date of birth will not jeopardise the privacy of Personally Identifiable Information (PII), only a partial date of birth (YYYY) will be collected. As the date and month will be missing, the date will be replaced by the June 30th of the year.

9.1.2. Immunogenicity

[figure not shown]
9.1.2.1. Humoral immune response

- A seronegative subject is a subject whose Ab concentration is below the cut-off value.
- A seropositive subject is a subject whose Ab concentration is greater than or equal to the cut-off value.
- The seropositivity rate is defined as the percentage of seropositive subjects.
- The VRR for anti-gE Ab concentration is defined as the percentage of subjects who have at least:
 - a 4-fold increase in the post last vaccination anti-gE Ab concentration as compared to the pre-vaccination anti-gE Ab concentration, for subjects who are seropositive at baseline, or,
 - a 4-fold increase in the post last vaccination anti-gE Ab concentration as compared to the anti-gE Ab cut-off value for seropositivity, for subjects who are seronegative at baseline.
- The GMC calculations are performed by taking the anti-log of the mean of the log base 10 concentration transformations. For descriptive statistics only, Ab concentrations below the cut-off of the assay will be given an arbitrary value equal to half the cut-off for the purpose of GMC calculation.
- To assess the VRR and the percentages of subjects with fold increase for anti-gE antibody concentration/ CD4+/CD8+ T-cells at Month 2/Month 3, subjects who are part of both PPS immunogenicity (Month 2/Month 3) and PPS immunogenicity at Day 1 will be considered.

CONFIDENTIAL

204939 (ZOSTER-062)

CCI

9.1.3. HZ incidence

- For the primary analysis of HZ incidence, first confirmed HZ episode will be considered.
- The HZ onset date is the earlier of the following two events: 1) the HZ rash start date; or 2) the date on which pain at the site of a subsequent HZ rash is first noted.
- A suspected case of HZ can be confirmed by GSK in two ways:
 - **By PCR:** Rash lesion samples will be collected from subjects clinically diagnosed as having a suspected case of HZ. The samples will be transferred to GSK or a validated laboratory designated by GSK Biologicals and analyzed using standardized and validated procedures for laboratory diagnosis of HZ by PCR (see Section 4.5.2.2.1 of the protocol).
 - **By the HZ Ascertainment Committee (HZAC):** All suspected HZ cases will be referred to the HZAC. The HZAC will classify all referred cases as either “HZ” or “not HZ” or “not able to decide” (see Section 4.5.2.2.2 of the protocol). The HZAC classification will serve as the final case definition only when the case cannot be confirmed or excluded by PCR. Therefore, definitive PCR results, when available, will determine the final HZ case assignment. In such cases, the HZAC classification will not contribute to HZ case determination decision
- For a given subject and for HZ episode, missing or non-evaluable measurements will not be imputed for the primary analysis. The missing endpoint and censoring are considered to occur independently, and the pattern being either Missing Completely At Random (MCAR) or Missing At Random (MAR) only.
- For HZ recurrence analysis, due to the algorithm used and taking into account both laboratory and HZAC results, no imputation and no sensitivity analysis for missing data will be performed.
- A 28-day pain-free period is used to confirm cessation of HZ-associated pain
- The “follow-up time at risk” for confirmed HZ is expressed in days and is computed according to the following rules:
 - The start date of the follow-up time (start) will be computed as follows:
 - From the dose 1 administration date for the analysis on the ES;
 - From 30 days post-dose 2 date for the analysis on the mES.
 - The end date of the follow-up time (stop) will be computed as follows:
 - Date of the last visit/contact for subjects who did not have an event;
 - Last contact date for subjects dropped out of the study, if not preceded by an event;
 - Date of the event
 - Date of HZ vaccination outside the study, if not preceded by an event

- The follow-up time at risk is computed using the following formula:
 - **stop – start +1.**

The **time at risk** will be expressed in Person-Year and derived from the follow up time (follow up time in days/365.25).

9.1.4. Safety

- For the analysis of **CCI** /HZ related complications/solicited AEs/unsolicited AEs/SAEs/pIMDs/ concomitant medication, all vaccinated subjects will be considered and subjects who did not report an event will be considered as subjects without an event.
- AEs that need to be reported as pIMDs are listed in Table 20 of the protocol.
- The maximum intensity of local injection site redness/swelling will be graded as:

[figure not shown]
0	<20 mm diameter
1	≥20 mm to – ≤50 mm diameter
2	>50 mm to – ≤ 100 mm diameter
3	>100 mm diameter

- The fever grading to be considered for analysis will be:

0	<38.0°C
1	≥38.0°C – ≤38.5°C
2	>38.5°C – ≤ 39.0°C
3	>39.0°C

- **CCI** [REDACTED]. Severe ‘worst’ pain is defined as HZ-associated pain rated as 3 or greater on the “worst pain” question on the Zoster Brief Pain Inventory (ZBPI) questionnaire (see Sections 6.4.1 and 4.5.2.1 of the protocol). **CCI** [REDACTED]. The cases without severe “worst” pain (score ≥ 3) were considered as non-event case.
- **CCI** [REDACTED]

CCI

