#### **6.6.14. Recording of AEs, SAEs, pregnancies and pIMDs**

- Refer to Section [9.3](#) for procedures for the investigator to record AEs, SAEs, pregnancies and pIMDs. Refer to Section [9.4](#) for guidelines and how to report SAE, pregnancy and pIMD reports to GSK Biologicals.
- The subjects /subject's LAR(s)/caregiver will be instructed to contact the investigator immediately should they manifest any signs or symptoms they perceive as serious.
- At each vaccination visit, diary cards will be provided to the subject/subject's LAR/caregiver. The subject will be instructed to measure and record the oral body temperature and any solicited local/general AEs (that is, on the day of vaccination and during the next 6 days) or any unsolicited AEs (that is, on the day of vaccination and during the next 29 days occurring after vaccination). The subject will be instructed to return the completed diary card to the investigator at the next study visit.
- Any unreturned diary cards will be sought from the subject through telephone call(s) or any other convenient method.
- The investigator will transcribe the collected information into the eCRF in English.

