## 11.6. Derived and transformed data

### 11.6.1. Handling of missing data

For the analysis of solicited AEs, missing or non-evaluable measurements will not be replaced. Therefore, the analysis of the solicited AEs based on the ES will include only subjects/doses with documented safety data (that is symptom screen/sheet completed).

For the analysis of HZ recurrence/unsolicited AEs/SAEs/pIMDs/concomitant medication, all vaccinated subjects will be considered and subjects who did not report an event will be considered as subjects without an event.

For a given subject and a given immunogenicity measurement, missing or non-evaluable measurements will not be replaced. Therefore, an analysis will exclude subjects with missing or non-evaluable measurements.

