4.1.3. Exposed Set

The exposed set (ES) will include all subjects with at least one study vaccine administered.

The ES for analysis of immunogenicity will include all vaccinated subjects for whom data related to immunogenicity endpoints are available. CCI

[REDACTED]

[REDACTED]

The ES for analysis of reactogenicity (e.g., solicited AEs) will include all subjects with at least one vaccine administration documented and who have solicited safety data (i.e., symptom screen/sheet completed).

The ES for analysis of safety (e.g. SAEs) will include all subjects with at least one vaccine administered.

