10.1.2.3. Daily recording of solicited adverse events

10.1.2.3.1. Studies with paper diaries

For studies using paper diaries which have questions in the CRF indicating the presence or absence of solicited AEs, the following rules are applicable.

Denominators for the summary of local (or general) solicited AEs will be calculated using the number of subjects who respond “Yes” or “No” to the question concerning the occurrence of local (or general) AEs.

When a specific solicited AE is marked as having not occurred following a specific vaccination (i.e. SDTM CE.CEOCCUR=N for the specified post-vaccination period for the AE in question), all daily measurements will be imputed as Grade 0.

When a specific solicited AE is marked as having occurred following a specific vaccination (i.e. SDTM CE.CEOCCUR=Y for the specified post-vaccination period for the AE in question), any missing daily recordings will be given imputed values to allow them to contribute to the ‘Any’ rows but not to specific grade rows of the solicited AE summary tables.

When the occurrence of a specific solicited AE is not present (i.e. SDTM CE.CEOCCUR is neither Y nor N for the specified post-vaccination period for the symptom in question) but the group of solicited AE (local or general) is marked as having occurred (i.e. SDTM CE.CEOCCUR=Y), all missing daily recordings will be given imputed values to allow them to contribute to the ‘Any’ rows but not to specific grade rows of the solicited AE summary tables.

The following table shows how subjects contribute to each category for a specific solicited AE over the Day X to Day Y post-vaccination period:

Solicited adverse event category	Subjects included in the calculation of the numerator
Any	All subjects with at least one occurrence of the adverse event at grade 1, grade 2, or grade 3 between Day X and Day Y or with the adverse event marked as present and at least one missing daily recording between Day X and Day Y
At least grade 1	All subjects with at least one occurrence of the adverse event at grade 1, grade 2, or grade 3 between Day X and Day Y
At least grade 2	All subjects with at least one occurrence of the adverse event at grade 2 or grade 3 between Day X and Day Y
At least grade 3	All subjects with at least one occurrence of the adverse event at grade 3 between Day X and Day Y

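### SAP 9.1.4 counts vaccinated subjects with no solicited AE data as reaction-free, against Protocol 11.6.1, SAP 4.1.3 and SAP 10.1.2.3.1

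*SAP*

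**What the plan says.** The first bullet of SAP 9.1.4 (Safety) sets a missing-data rule for a list of outcomes: for "HZ related complications/solicited AEs/unsolicited AEs/SAEs/pIMDs/ concomitant medication, all vaccinated subjects will be considered and subjects who did not report an event" are counted as not having had one. Solicited AEs are in the list.

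Three other places treat solicited AEs differently.

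- Protocol 11.6.1: "For the analysis of solicited AEs, missing or non-evaluable measurements will not be replaced", and so "the analysis of the solicited AEs based on the ES will include only subjects/doses with documented safety data". That section has its own rule that no report means no event. It begins "For the analysis of HZ recurrence/unsolicited AEs/SAEs/pIMDs/concomitant medication, all vaccinated subjects will be considered", and solicited AEs are not in it.
- SAP 4.1.3 defines the Exposed Set for reactogenicity as subjects with a documented vaccination and "who have solicited safety data (i.e., symptom screen/sheet completed".
- SAP 10.1.2.3.1: "Denominators for the summary of local (or general) solicited AEs will be calculated using the number of subjects who respond" Yes or No on whether such events occurred.

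SAP Section 8 lists departures from the protocol, including one as small as the fever grading. It does not list this one.

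**The concern.** The passages give different denominators for the same tables. For unsolicited events and SAEs, silence is conventionally read as no event. For solicited AEs the subject is asked about each event directly, so an absent symptom screen is missing data rather than a negative answer.

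If the 9.1.4 sentence is programmed as it stands, a subject with no symptom screen is tabulated as having had no pain, no fever and no other reaction. Every solicited AE percentage then falls relative to the protocol's rule, and none can rise. Solicited AEs are a named secondary endpoint (SAP 2.2.2), and the final analysis feeds the study report and public posting (SAP 7.1).

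**Working it through.** **Which rule prevails.** The introduction to SAP Section 9 confines that section to rules not given in 10.1, which suggests that 10.1.2.3.1 was meant to stand. The introduction to SAP 10.1 says its rules apply together with the study-specific ones in Section 9. Neither states an order of precedence, so a programmer must infer one.

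**Inputs.** N = 713 per group (Protocol 11.4), all taken as vaccinated. The plan gives no solicited AE rate and no share of missing screens, so there is no stated figure to reproduce. The following are assumptions:

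- p, the rate among subjects with solicited data
- m, the share of vaccinated subjects without solicited data
- q, the unobserved rate among those without data

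**Formula.** Subjects with data number N(1−m), and events number p × N(1−m). Over subjects with data the rate is p. Over all N, with non-reporters as event-free, it is p × N(1−m)/N = p(1−m). The relative fall is m and the absolute fall is p × m.

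**Counts at N = 713.** Subjects without data are 713m rounded; events are p times the number with data, rounded. Falls are computed before the percentages are rounded.

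| m | Without / with data | p = 80%: events, documented → literal | Fall (points) | p = 15%: events, documented → literal | Fall (points) |
|---|---|---|---|---|---|
| 1% | 7 / 706 | 565, 80.0% → 79.2% | 0.8 | 106, 15.0% → 14.9% | 0.1 |
| 2% | 14 / 699 | 559, 80.0% → 78.4% | 1.6 | 105, 15.0% → 14.7% | 0.3 |
| 5% | 36 / 677 | 542, 80.1% → 76.0% | 4.0 | 102, 15.1% → 14.3% | 0.8 |
| 10% | 71 / 642 | 514, 80.1% → 72.1% | 8.0 | 96, 15.0% → 13.5% | 1.5 |

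At p = 80% and m = 5%, the exact 95% CI is 76.8% to 83.0% for 542/677, and 72.7% to 79.1% for 542/713.

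**Between groups.** With the same m in both groups the rate ratio is unchanged and the difference shrinks by the factor (1−m). Assumed rates of 80% and 15% with m = 5% give 0.95 × 65.0 = 61.75 points instead of 65.0. With unequal m the ratio also moves. Assumed rates of 80% and 20%, with m = 10% on HZ/su and 5% on placebo, give (0.80 × 0.90)/(0.20 × 0.95) = 0.72/0.19 = 3.79 instead of 4.00.

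**How much of the fall is bias.** The true rate over all vaccinated subjects is p(1−m) + qm. The literal rule errs by −qm and the documented-data rule by (p−q)m. At p = 80%, m = 5% and q = 40% the true rate is 76.0 + 2.0 = 78.0%. The literal rule gives 76.0% (error −2.0 points) and the documented-data rule 80.0% (error +2.0 points).

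**What a single m leaves out.** The share without data can differ by group, by dose, and between local and general events. Results are tabulated after each dose (SAP 5.5.1), and Protocol 7.5 foresees subjects who do not receive dose 2. A literal reading of all vaccinated subjects could count them as reaction-free after a dose they never had. Also, where the local or general question is answered Yes but one specific event is blank, SAP 10.1.2.3.1 counts the subject in the 'Any' row, whereas 9.1.4 could count no event.

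**The case against.** The strongest reply is that the plan already settles this. Solicited AEs have their own analysis set in SAP 4.1.3, and 10.1.2.3.1 is the detailed programming rule, with denominator, data flag and numerator table. If 9.1.4 is read only within the 4.1.3 set it does no harm: it merely repeats that when a subject marks an event as not having occurred, "all daily measurements will be imputed as Grade 0". That reading is reasonable and probably the intended one. But 9.1.4 speaks of all vaccinated subjects, and nothing says that it yields to the other sections. The table layouts are in a separate document (SAP 10.2), so how it was programmed cannot be seen.

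Second, the sizes are hypothetical. That stands. The protocol also provides that "Any unreturned diary cards will be sought from the subject through telephone call(s) or any other convenient method", so the rows at 5% and 10% may be pessimistic.

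Third, a lower rate is not necessarily a worse one. That also stands: the two errors are equal in size at q = p/2, and below that the literal rule is nearer the truth. The objection to 9.1.4 is that it contradicts the prespecified rule without saying so, not that it is always the more biased.

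Fourth, the other passages are not identical. Protocol 11.5.1 defines the reactogenicity set without requiring solicited data, and 11.6.1 adds that restriction. SAP 10.1.2.3.1 uses a Yes/No answer, separately for local and general events, and lets missing daily recordings count in the 'Any' row. These are differences of detail. Protocol 11.6.1 and the two SAP sections still agree that a subject with no solicited data is left out.

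**Conclusion.** The rule in SAP 9.1.4 is wrong as written for solicited AEs. The contradiction is certain from the texts; that it is a drafting slip is an inference, though a likely one. Taken literally, the rule multiplies every solicited AE rate by (1−m). In absolute terms the change is p × m, and its size depends wholly on values that the documents do not give. If follow-up of diary cards keeps m near 1% to 2%, a reaction with a rate of 80% moves by 0.8 to 1.6 points and one with a rate of 15% by 0.1 to 0.3 points. The analyses concerned are descriptive (SAP Section 6). The correction should be made because it is clear-cut and almost free, not because the likely effect is large.

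**What to change.** 1. Delete 'solicited AEs' from the list in the first bullet of SAP 9.1.4.
2. Add one sentence there: *Solicited AE tables follow Sections 4.1.3 and 10.1.2.3.1; missing symptom screens are not replaced.*
3. Optionally, show the number of subjects and doses without a completed symptom screen, by group and dose.

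The cost is two words removed and one sentence added, with no new data and no new analysis. The denominator then agrees with Protocol 11.6.1 in leaving out subjects without solicited data. The trade-off is that if non-completers had fewer reactions than completers, the documented-data rule overstates rates by (p−q)m. The optional count lets a reader judge how large that could be.

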9.2. Statistical Method

9.2.1. HZ incidence

The number of HZ incidence is assumed to follow the Poisson distribution. The estimated incidence rate with 95% CI for both groups will be computed using following formula:

Incidence rate (per 1000) = Number of events*1000/Total follow-up period (in days)
=n*1000/T

$$\text{Exact LL of incidence rate} = \frac{X_{2n,\alpha/2}^2}{2T}$$

$$\text{Exact UL of incidence rate} = \frac{X_{2(n+1),(1-\frac{\alpha}{2})}^2}{2T}$$

Where $X_{v,\alpha}^2$ is the chi-square distribution quantile for upper tail probability on v degrees of freedom, n is the number of events and T is the total follow-up time [Ulm, 1990]. Rule to derive the total follow-up period (in days) is provided in section 9.1.3 of the SAP.

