## 11.4. Determination of sample size

The sample size determination enables the evaluation of the non-inferiority of HZ recurrence incidence rate, and to rule out a 5-fold increased risk of HZ recurrence in the HZ/su group compared to the placebo group. The following assumptions were made:

- Incidence rate of HZ recurrence in the placebo group= 0.55% per year.
- Incidence rate of HZ recurrence in the HZ/su group= 0.275% per year, assuming a 50% vaccine efficacy.
- Power of 90% and Type I error of 0.025 (one-sided).
- Criterion for non-inferiority = 5-fold; the 5-fold criterion has been selected as acceptable for ruling out a moderate increased risk of HZ in a clinical trial setting.

Let  $\pi$  be the ratio of incidence rate of HZ recurrence in HZ/su group vs the placebo group, then null hypothesis  $H_0: \pi \geq 5$  vs. alternative hypothesis  $H_a: \pi < 5$ . With the assumption that the number of HZ recurrence cases in HZ/su and placebo group follows Poisson distribution independently, conditioning on the total number of cases, the number of cases in HZ/su group would follow the binomial distribution [Lehmann, 1959]. With 1:1 randomization, the parameter  $p$  in the binomial distribution (that is, the probability of HZ recurrence in HZ/su group) is expected to be  $p=\pi/(1+\pi)$ . Therefore, the above hypotheses becomes:  $H_0: p \geq 0.8333$  vs.  $H_a: p < 0.8333$ . Under the assumption of VE of 50%, a total number of 10 HZ recurrence cases is needed (PASS 12: Tests for One Proportion using proportions (Exact Test)). With incidence rate of 0.55% per year and two year follow up, 606 evaluable subjects per group are needed. Further assuming a dropout rate of 15% during the 2 year follow up period, 713 subjects per group (a total of 1426 subjects) need to be enrolled.

CCI

A large black rectangular redaction box covers the majority of the page content below the CCI label, starting from the bottom of the CCI label and extending down to just above the section 11.4.2 header.

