5.3.1.1. Within group

For each group, the number of subjects, person-time, number of confirmed HZ cases and incidence rate will be tabulated from 30 days post the last vaccination until study end and from first study vaccination until study end on ES.

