5.3.2. Additional considerations

For analysis for non-inferiority, only the first confirmed HZ episode will be considered. The non-inferiority will be assessed by following model and fitted via the PROC GENMOD procedure according to the following code:

```
PROC GENMOD data=XXX;
  CLASS group_nb(ref="Placebo") / param=ref;
  MODEL nb_cases = group_nb / dist=poisson offset=log_T link=log type3;
```

```

EXACT group_nb / estimate=odds;
ODS OUTPUT ExpExactParmEst=IRR;
RUN;

```

where,

nb_case = number of cases

Group_nb = Group information of the subject (treatment received by subject)

Log_T = Log of the follow-up time

Note: variables names may vary as per ADAM variables however their derivations remain the same.

The estimated rate ratio and its 95% CI will be provided in the output dataset IRR.

In extreme situations, when there are no confirmed HZ cases in the HZ/su group and > 0 confirmed HZ cases in the Placebo group, the EXACT computational algorithm used in SAS will run into difficulty and cannot provide accurate results. Therefore, the rate ratio (HZ/su versus placebo) will be set to 0. When there are no confirmed HZ cases in the Placebo group and > 0 confirmed HZ cases in the HZ/su group, the rate ratio is not estimable, instead the incidence rate and 95% CI in each treatment group will be reported.

- For Bayesian analysis, the number of HZ cases in the HZ/su and in placebo groups follows Poisson distribution with rate (incidence rate) of λ_{HZ} and λ_P , respectively. We further assume that λ_{HZ} and λ_P are random variables both with non-informative Gamma prior distribution: Gamma (0.001, 0.001). The posterior distribution of λ_{HZ} and λ_P will be Gamma distribution with parameter

$\lambda_{HZ} \sim \text{Gamma}(0.001 + case_{HZ}, 0.001 + T_{HZ})$ and

$\lambda_P \sim \text{Gamma}(0.001 + case_P, 0.001 + T_P)$

where,

$case_{HZ}$ = number of cases in HZ/su group

$case_P$ = number of cases in placebo group

T_{HZ} = total follow-up time in years in HZ/su group

T_P = total follow-up time in years in placebo group

To estimate the probability of incidence rate ratio, simulation program will be run to generate sample from Gamma distribution using the function above.

The probability of incidence rate ratio greater than a specified value (e.g., 1, 2, 3, 4, 5) will be plotted against incidence rate ratio in graph.

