9.2.2. Safety

The ~~CI~~ and other HZ related complication is assumed to follow Poisson distribution and will be estimated for both the groups with 95% CI using the formula provided in the section 9.2.1 of the SAP.

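### SAP 9.2.1 computes the per-group HZ incidence rate on follow-up in days under a label with no time unit, while SAP 9.1.3 and the other HZ analyses work in years; the two scales differ by a factor of 365.25.

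*SAP*

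**What the plan says.** SAP 9.2.1 sets out the estimated incidence rate and its 95% CI for both groups. The point estimate is "Incidence rate (per 1000) = Number of events*1000/Total follow-up period (in days"), shortened to n*1000/T. The section repeats the unit: "Rule to derive the total follow-up period (in days) is provided in section 9.1.3 of the SAP". The exact limits are chi-square quantiles divided by 2T, with no factor of 1000.

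SAP 9.1.3 defines two quantities. Follow-up time at risk "is expressed in days and is computed according to the following rules". Time at risk then "will be expressed in Person-Year and derived from the follow up time (follow up time in days/365.25").

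Other places that use or report follow-up time:

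- SAP 5.3.1.2 and Protocol 11.8 define total follow-up in the non-inferiority analysis in years.
- SAP 5.3.2 defines the Bayesian exposure as "total follow-up time in years in HZ/su group", and likewise for placebo.
- Protocol 11.4 sizes the trial on annual rates: "Incidence rate of HZ recurrence in the placebo group= 0.55% per year".
- SAP 5.3.1.1 says that, for each group, the number of subjects, "person-time, number of confirmed HZ cases and incidence rate will be tabulated". It gives no unit for person-time.
- SAP 9.2.2 estimates HZ-related complications "using the formula provided in the section 9.2.1 of the SAP".

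**The concern.** The one formula a programmer would use for the HZ rate has a denominator in days, and every between-group HZ analysis and planning assumption is in years. Because the label says only per 1000, nothing in the output would show which unit had been used.

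Three outputs depend on the formula:

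- **The per-group recurrence rates.** These are a secondary objective (SAP 2.1.2, Protocol 2.2). They are tabulated beside person-time and case counts. If person-time is shown in person-years, as 9.1.3 suggests, a day-based rate will not equal cases divided by the person-time in the same table.
- **The fallback in SAP 5.3.2.** If placebo has no cases and HZ/su has some, the ratio is declared not estimable, and the per-group rates with their CIs become the reported result.
- **The HZ-complication rates** under SAP 9.2.2.

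Readers will want to set these rates against the 0.55% per year in Protocol 11.4 and the figure of under 1% per year in Protocol 1.2.1, which made the recurrences in the earlier uncontrolled study unexpected. An unlabelled day-based rate invites a wrong comparison.

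**Working it through.** **Inputs (Protocol 11.4).** Placebo rate 0.0055 per year; HZ/su rate 0.00275 per year; margin 5; one-sided alpha 0.025; power 90%; 1:1 allocation; 10 cases; 2 years of follow-up; 606 evaluable per group; 15% dropout; 713 enrolled per group. Conversion: 365.25 days per person-year (SAP 9.1.3).

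**Step 1: reproduce the plan's figures.** Conditional on the total number of cases, p0 = 5/6 and p1 = 0.5/1.5 = 1/3. With 10 cases the exact test rejects at 5 or fewer in HZ/su, with alpha 0.0155 and power 0.923. With 9 cases the power is 0.855, so 10 is the smallest number reaching 90%.

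- Evaluable N per group = 10 / [2 × (0.0055 + 0.00275)] = 606.06, so 606.
- Enrolled N per group = 606 / 0.85 = 712.9, so 713.

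All the stated figures reproduce, and they do so with rates per year.

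**Step 2: the rate in each unit.** Per group, 606 × 2 = 1,212 person-years, and 1,212 × 365.25 = 442,683 person-days.

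| Group | Expected cases | n × 1000 / person-years | n × 1000 / days (9.2.1 as written) |
|---|---|---|---|
| Placebo | 1,212 × 0.0055 = 6.666 | 5.50 | 0.01506 |
| HZ/su | 1,212 × 0.00275 = 3.333 | 2.75 | 0.00753 |

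The quotient of the last two columns is 365.25 in both rows. On the same scale, 1% per year is 10 per 1000 person-years, or 10/365.25 = 0.0274 per 1000 person-days.

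**Step 3: the limits.** Take 7 placebo cases as an illustration, with the usual chi-square quantiles (2.5% for the lower limit, 97.5% for the upper).

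- Person-years, limits × 1000: 5.78 (95% CI 2.32 to 11.90) per 1000 person-years.
- Days, limits × 1000: 0.0158 (0.00636 to 0.0326) per 1000 person-days.
- As written, in days and without the 1000: point estimate 0.0158, limits 0.0000064 to 0.0000326. The interval does not contain its own estimate.

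Changing T to person-years would not cure this last mismatch. The limits would still be 1000 times too small relative to the estimate.

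**Step 4: the primary analysis.** With 3 HZ/su and 7 placebo cases and equal follow-up, the rate ratio is 0.429 with exact 95% CI 0.072 to 1.877. The result is identical with follow-up in years or in days, because the unit divides out.

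**The case against.** The strongest reply is that nothing is miscalculated. Read as printed, n*1000/T with T in days is a valid rate per 1000 person-days, and it converts to person-years by one multiplication. That stands. The defect is an inconsistent denominator with an incomplete label.

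A reader might infer that every tabulated HZ rate will come out 365.25 times too small. The documents do not support that. The rate is too small only if per 1000 is taken to mean per 1000 person-years, which 9.2.1 never says. Section 9.1.3 derives follow-up in days first and only then converts it, so the unit of the final tables is unsettled. The table layouts are in a separate document (SAP 10.2). Nor can one say that the rates would round to zero in print: SAP 10.1.4 has decimal rules for percentages, differences in percentages and geometric mean concentrations, but none for incidence rates.

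A reader might also infer that the primary conclusion is at risk. It is not, as step 4 shows, and the Bayesian analysis explicitly takes years.

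Finally, the 5.3.2 fallback is unlikely on the plan's assumptions. With 6.67 placebo cases expected, the probability of none is exp(−6.67), about 0.13%; at half that rate it is about 3.6%. Even then both groups would be on the same scale. This limits the weight of the fallback but leaves the secondary-objective rates and the 9.2.2 outputs as they are.

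The reply does not remove the conflict. Section 9.2.1 says days twice, it is the only incidence-rate formula in the SAP, and its reference to 9.1.3 is to the quantity in days. The text does not resolve itself.

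**Conclusion.** The point holds as an internal inconsistency. The 9.2.1 formula, followed literally, gives a rate per 1000 person-days with no unit on the label, while 9.1.3 and the other HZ analyses are in years. The factor is exactly 365.25: 0.0151 against 5.5 for placebo and 0.0075 against 2.75 for HZ/su. These figures rest on the planning rates and on 606 subjects per group each followed for 2 years; the factor itself rests only on the 365.25-day conversion.

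The scope is the descriptive per-group rates, the per-group rates reported when only placebo has no cases, and the HZ-complication rates. The primary rate ratio, the margin of 5 and the sample size are untouched. It should be corrected because these rates serve a secondary objective and will be read against annual figures, but it does not bear on the primary decision.

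**What to change.** In SAP 9.2.1:

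- Define T as total time at risk in person-years, that is, the sum of follow-up days divided by 365.25 as in 9.1.3. Remove both references to days.
- State the rate as n × 1000 / T and label it *per 1000 person-years*.
- Use the same T for both confidence limits and multiply each by 1000, so that the estimate and its interval share one scale.

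Section 9.2.2 then follows through its cross-reference. In 5.3.1.1, state that person-time is tabulated in person-years, so that the rate can be checked from the same table.

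The cost is a few lines of SAP wording, a table label and a check of the program. No new data or analyses are needed.
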